12.1.10.1. Hematology

Hematology analysis will include a complete blood count with differential and platelet count with smear. Samples will be collected and shipped in accordance with the laboratory manual provided by the central laboratory. Blood samples for hematology analysis will be collected as specified in the SoA ([Appendix 1](#)).

Immediate/same-day hematology analyses required during in-patient dosing, as determined by Investigator, will be performed as per investigational site standard procedures at the local laboratory. Investigators will receive hematology results from all trial visits from the central laboratory.

12.1.10.2. Blood Chemistry

Samples will be collected and shipped in accordance with the laboratory manual provided by the central laboratory. Blood samples for chemistry analysis will be collected as specified in the SoA ([Appendix 1](#)).

Immediate/same-day chemistry analyses required during in-patient dosing, as determined by Investigator, will be performed as per investigational site standard procedures at the local laboratory.

Chemistry analysis will include the following at all trial visits:

- Serum GGT
- AST/ALT
- Serum total bilirubin
- Direct bilirubin
- Albumin
- Glucose
- Creatinine kinase
- Creatinine
- BUN
- Electrolytes
- Alkaline phosphatase

CK-MB or Troponin I will be collected as specified in the SoA ([Appendix 1](#)) as applicable:

- Patients screened and dosed before IRB/EC approval of Protocol version 3.0 incorporating Amendment 2 will be tested for CK-MB throughout the study.
- Patients screened before IRB/EC approval of Protocol version 3.0 incorporating Amendment 2 but dosed afterwards will be tested for CK-MB at screening but for Troponin 1 at baseline and thereafter.
- Patients screened after IRB/EC approval of Protocol version 3.0 incorporating Amendment 2 will be tested for Troponin 1 from screening onwards.

Investigators will receive chemistry results from all trial visits from the central laboratory.

12.1.10.3. Urinalysis

Urine samples will be collected in accordance with the laboratory manual provided by the central laboratory as specified in the SoA ([Appendix 1](#)). Day -1 urinalysis will be processed locally in accord with local procedures. Urinalysis will include the following parameters:

- Color
- Clarity/turbidity
- pH
- Specific gravity
- Glucose
- Ketones
- Nitrites
- Leukocyte esterase

- Bilirubin
- Blood
- Protein
- Red Blood Cell
- White Blood Cell
- Squamous epithelial cells
- Casts
- Crystals
- Bacteria
- Yeast

12.1.10.4. Virus Serology

The administration of an AAV vector has the risk of causing immune-mediated hepatitis. For patients who have HIV or positive serology for hepatitis B or C, administration of AAV vector may represent an unreasonable risk; therefore, negative serology testing must be confirmed at screening, prior to treatment. These samples will be collected at screening ([Appendix 1](#)) and shipped in accordance with the laboratory manual provided by the central laboratory.

12.1.10.5. Capillary Blood Gas

Capillary blood gas will be completed locally at Day –1 and Day 2 ([Appendix 1](#)). A puncture or small incision will be made with a lancet or similar device into the cutaneous layer of the patient's skin at a highly vascularized area (heel, finger, toe). To accelerate blood flow and reduce the difference between the arterial and venous gas pressures, the area will be warmed prior to the puncture. As the blood flows freely from the puncture site, the sample will be collected in a capillary tube.

12.1.10.6. Immunology Testing (ELISA)

Blood samples for immunology testing will be collected and shipped to the central laboratory in accordance with the laboratory manual to test for serum antibodies to AAV9 and SMN (ELISA). Blood samples will be collected as specified in the SoA ([Appendix 1](#)).

12.1.10.7. AAV9 Antibody Screen in Biological Mother

There is potential that the biological mother of the patient may have pre-existing antibodies to AAV9 that may be transferred to the patient through breast milk or, theoretically, via placental transfer in utero. Informed consent will be requested from the biological mother of the patient to screen the biological mother for circulating antibodies to AAV9. Once informed consent has been obtained, the biological mother will have her blood drawn from a peripheral vein at screening and shipped to the central laboratory for screening of anti-AAV9 antibodies. Patients whose biological mothers are involved with their care but do not consent to AAV9 antibody screening are not eligible to participate.

If AAV9 antibodies are identified, the Investigator should discuss with the biological mother whether to continue or to stop breast feeding. Patients consuming banked breast milk from donor sources that cannot be test for anti-AAV9 antibodies must be transitioned to formula prior to participation.

12.1.10.8. Blood for Diagnostic Confirmation Testing

A blood sample will be collected during the screening visit and shipped to the central laboratory in accordance with the laboratory manual for reconfirmation of *SMN1* deletions/mutations, *SMN2* copy number, and absence or presence of exon 7 gene modifier mutation (c.859G>C).

This will be done to ensure consistency in diagnostic testing practices.

12.1.10.9. Saliva, Urine, and Stool Collection

Studies have shown that some vector can be excreted from the body for a few weeks after injection; this is called “viral shedding.” Vector shedding can be found in the blood, urine, saliva, and stool for up to a few weeks following infusion. The risks associated with the shed vector are not known at this time; however, the risk is thought to be low as the vector cannot replicate. Regardless, IRB/IEC- approved instructions should be provided to the patient’s family and care giver(s) regarding use of protective gloves if/when they come into direct contact with the patient’s bodily fluids and/or waste, as well as good hand-hygiene for a minimum of 4 weeks after gene replacement therapy. Additionally, patients are prohibited from donating blood for 2 years following the vector infusion.

Saliva, urine, and stool samples will be collected for viral shedding studies as specified in the SoA ([Appendix 1](#)). Samples will be collected, prepared, and shipped as per the laboratory manual.

13. ADVERSE AND SERIOUS ADVERSE EVENTS

13.1. Definition of Adverse Events

13.1.1. Adverse Event

An AE is the development of an undesirable medical condition or the deterioration of a pre-existing medical condition following or during exposure to a pharmaceutical product, whether or not considered casually related to the product. In clinical studies, an AE can include an undesirable medical condition occurring at any time, including baseline or washout periods, even if no trial treatment has been administered.

All AEs (related or not related) that occur after signing of the informed consent through the last trial visit will be collected and recorded in the eCRF.

All AEs will be classified in accordance with the CTCAE version 4.03 outlined in [Table 4](#).

Table 4: Common Terminology Criteria for Adverse Events

Grade	Definition
1	Mild; asymptomatic or mild symptoms; clinical or diagnostic observations only; intervention not indicated
2	Moderate; minimal, local or noninvasive intervention indicated; limiting age-appropriate instrumental ADL. ^a
3	Severe or medically significant, but not immediately life-threatening; hospitalization or prolongation of hospitalization indicated; disabling; limiting self-care ADL. ^b
4	Life-threatening consequences; urgent intervention indicated.
5	Death related to AE.

Source: Common Terminology Criteria for Adverse Events (version 4.03) [40]

^a Instrumental ADL refer to preparing meals, shopping for groceries or clothes, using the telephone, managing money, etc.

^b Self-care ADL refer to bathing, dressing and undressing, feeding self, using the toilet, taking medications, and not bedridden.

Additionally, a DSMB/DMC will review safety data on a quarterly basis. A detailed description of the DSMB/DMC, its role in this trial, and the timing and process of the scheduled reviews will be described in a DSMB/DMC Charter.

13.1.2. Serious Adverse Event

A serious adverse event (SAE) is an AE occurring during any trial Phase (i.e., baseline, treatment, washout, or follow-up), and at any dose of the investigational product, or comparator that fulfils ≥ 1 of the following:

- Results in death
- It is immediately life-threatening
- It requires in-patient hospitalization or prolongation of existing hospitalization
- Results in persistent or significant disability or incapacity

- Results in a congenital abnormality or birth defect
- It is an important medical event that may jeopardize the patient or may require medical intervention to prevent one of the outcomes listed above.

All SAEs (related and not related) that occur after signing of the informed consent through 30 days after the last trial visit will be collected and recorded on forms provided by AveXis within 24 hours of the site becoming aware.

13.1.3. Adverse Events of Special Interest

The following are considered AEs of special interest (AESIs):

- Hepatotoxicity
- Thrombocytopenia
- Cardiac adverse events
- Sensory abnormalities suggestive of ganglionopathy

All AESIs (related and not related) that occur after signing of the informed consent through 30 days after the last study visit, irrespective of grade, should be collected and recorded on forms provided by AveXis within 24 hours of the site becoming aware.

13.2. Relationship to Trial Drug

An Investigator who is qualified in medicine must make the determination of relationship to the investigational product for each AE (Unrelated, Possibly Related, Probably Related, or Definitely Related). The Investigator should decide whether, in his or her medical judgment, there is a reasonable possibility that the event may have been caused by the investigational product. If no valid reason exists for suggesting a relationship, then the AE should be classified as “unrelated.” If there is any valid reason, even if undetermined, for suspecting a possible cause-and-effect relationship between the investigational product and the occurrence of the AE, then the AE should be considered “related.”

If the relationship between the AE/SAE and the investigational product is determined to be “possible” or “probable” then the event will be considered related to the investigational product for the purposes of expedited regulatory reporting.

13.3. Recording Adverse Events

Adverse events spontaneously reported by the patient and/or in response to an open question from the trial personnel or revealed by observation will be recorded during the trial at the investigational site. Information about AEs (related and not related) after signing of the informed consent form through the last study visit are to be collected. Serious adverse event information will be collected after signing of the informed consent form through 30 days after the last study visit. The AE term should be reported in standard medical terminology when possible. For each AE, the Investigator will evaluate and report the onset (date and time [if start date during inpatient period]), resolution (date and time [if start date during inpatient period]),

intensity, causality, action taken, serious outcome (if applicable), and whether or not it caused the patient to discontinue the trial.

It is important to distinguish between serious and severe AEs. Severity is a measure of intensity whereas seriousness is defined by the criteria under [Section 13.1.2](#). An AE of severe intensity may not be considered serious.

13.4. Reporting Adverse Events

All SAEs (related and unrelated) will be recorded from signing of consent form through 30 days after the last trial visit. Any SAEs considered possibly, probably, or definitely related to the investigational product and discovered by the Investigator at any time after the trial should be reported. All SAEs must be reported to AveXis or designee within 24 hours of the first awareness of the event. The Investigator must complete, sign and date the SAE pages, verify the accuracy of the information recorded on the SAE pages with the corresponding source documents, and send a copy by fax or e-mail to AveXis or designee. Note: elective procedures or minor surgeries where hospitalization is required should not be reported as SAEs.

Additional follow-up information, if required or available, should all be faxed or e-mailed to AveXis or designee within 24 hours of receipt and this should be completed on a follow-up SAE form and placed with the original SAE information and kept with the appropriate section of the eCRF and/or trial file.

AveXis is responsible for notifying the relevant regulatory authorities of certain events. It is the Principal Investigator's responsibility to notify the IRB/IEC of all SAEs that occur at his or her site. Investigators will also be notified of all unexpected, serious, drug-related events (7/15 Day Safety Reports) that occur during the clinical trial. Each site is responsible for notifying its IRB/IEC of these additional SAEs.

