12.1.8. Swallowing Test

A standard bedside, non-barium (unless required per institutional policy), swallowing test will be performed as specified in the SoA ([Appendix 1](#)) to determine if the patient has signs of aspiration. The swallowing test at Screening can be performed at the investigator site. If the test is positive for aspiration, there may be a recommendation for the patient to use an alternate method to oral feeding for the duration of the trial at the determination of the Investigator and treating clinician.

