2.2.2. DSMB Reporting and Meetings

Reports describing the status of the study will be prepared by AveXis and sent to each DSMB member prior to each meeting for review and preparation. DSMB meetings will occur on quarterly basis, aligning with the AveXis quarterly data cut reviews (as AVXS summary report completed in following month).

Reports include the following:

- A brief narrative of the study status, including the target enrollment, current and projected time to completing enrollment. Any significant events and/or difficulties should be briefly described in this narrative.
- A brief narrative for each participant describing gender, age, race and ethnicity and other relevant demographic characteristics. The narrative for each participant should briefly describe his/her study status (i.e., dose level, visit number, adverse event information).
- A timeline outlining the study progress relative to visit number for each participant, as well as time points for each SAE/Dose Limiting Toxicity. A total for Adverse Events (AEs) for each participant should be included.
- A summary of AEs by grade levels
- A listing of AE details grouped by participant
- A listing of SAE details grouped by participant
- A listing of deaths
- A summary of clinically significant laboratory test results
- Other key information related to safety/conduct of the study

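### The note in Protocol Section 13.4 exempts hospitalised elective procedures and minor surgery from SAE reporting without limits; read literally it conflicts with Section 13.1.2, and true SAEs could go unreported

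*Protocol*

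**What the plan says.** Protocol Section 13.1.1 defines an adverse event through the medical condition: "An AE is the development of an undesirable medical condition or the deterioration of a pre-existing medical condition following or during exposure". Section 13.1.2 lists what makes an AE serious, and one criterion is: "It requires in-patient hospitalization or prolongation of existing hospitalization". No surgical exception is attached. Section 13.3 confirms which section governs: "Severity is a measure of intensity whereas seriousness is defined by the criteria under" Section 13.1.2.

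Section 13.4 opens with a general rule, "All SAEs (related and unrelated) will be recorded from signing of consent form through 30 days after the last trial visit", and requires SAEs to reach the sponsor within 24 hours of first awareness. The same paragraph ends: "Note: elective procedures or minor surgeries where hospitalization is required should not be reported as SAEs".

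The note does not define minor surgery, sets no condition on when the procedure was planned, and does not mention the condition that made it necessary. No other part of the protocol or SAP supplies these limits.

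**The concern.** A seriousness rule and its reporting rule should pick out the same events. Here the reporting rule carries an exemption that the definition lacks. A narrow exemption, for an admission arranged in advance for a stable pre-existing problem, would fit the definition, because no new or worsened condition is involved. This one is broader. Because its two limbs are joined by an alternative, a minor operation need not be elective to be exempt, and an unplanned one prompted by a post-dose event falls within the words.

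At stake are the processes that start from SAE status: the 24-hour report, notification of the IRB/IEC by the principal investigator, SUSAR assessment, the DSMB's SAE listing and the serious-TEAE tables. The trial has no concurrent control arm whose data would be subject to the same misclassification, and any error caused by the note can only be towards too few SAEs.

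**Working it through.** The plan gives no figure on this point, so the check is a comparison of texts applied to one test case.

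**Test case.** After dosing, an infant develops a new condition, or an existing one worsens. It is not an AESI and meets no other seriousness criterion. The infant is admitted for minor surgery to deal with it.

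**Step 1, definition.** The condition is an AE under 13.1.1. The admission makes it an SAE under 13.1.2, which 13.3 names as the governing section.

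**Step 2, reporting.** The note in 13.4 allows two readings:
- *Literal reading:* the hospitalization criterion is switched off for minor surgery, and nothing is reported as an SAE.
- *Narrow reading:* the operation is not the SAE, but the condition still is.

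**Step 3, consequences.**

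| Route | Source | Definition / narrow reading | Literal reading |
|---|---|---|---|
| 24-hour report to sponsor | Protocol 13.1.2, 13.4 | Yes | No |
| IRB/IEC notification | Protocol 13.4 | Yes | No |
| SUSAR assessment | Protocol 13.5 | Yes | Not reached |
| DSMB listing: "A listing of SAE details grouped by participant" | SAP 2.2.2 | Yes | No |
| Serious-TEAE tables (onset up to last visit) | SAP 10.3.1, 10.3.2 | Yes | No |
| AE record, up to last visit | Protocol 13.1.1, 13.3 | Yes | Yes, as non-serious |
| Any record in the 30 days after last visit | Protocol 13.1.2, 13.3, 13.4 | Yes | None required |

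The last row follows from the collection periods: ordinary AEs stop at the last visit, while SAEs and AESIs continue for 30 more days.

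**Step 4, is the test case foreseeable?** Section 12.1.8 says that after a positive swallowing test "there may be a recommendation for the patient to use an alternate method to oral feeding for the duration of the trial". It mentions neither surgery nor admission. However, SAP 4.6.5 describes non-oral feeding support as something implanted, Protocol 14.1.1.1.3 counts a need for gastrostomy against an exploratory endpoint, and Protocol 5.5 names infection at the infusion site as possible. Neither feeding problems nor local infusion-site problems are as such on the AESI list (hepatotoxicity, thrombocytopenia, cardiac events, sensory abnormalities suggesting ganglionopathy). The case is plausible, but the documents do not show how often it would occur.

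**Step 5, size.** With 30 treated infants, one infant whose only SAE was exempted would lower SAE incidence by 1/30 = 3.3 percentage points. An infant with another SAE would change it by nothing. The documents give no count to multiply by.

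**The case against.** The strongest reply is that the note concerns procedures, whereas the definitions concern conditions. With 13.3 pointing to 13.1.2 and the same paragraph of 13.4 requiring all SAEs to be recorded, a careful site would report the condition and leave out only the operation. This stands as an available reading. A reader might infer from the note that admissions caused by post-dose events would not be reported, but the documents support only that some could be missed. The note also reaches only admissions for elective procedures or minor surgery, and an event that meets another seriousness criterion is an SAE through that criterion.

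The narrow reading does not remove the problem. Under 13.1.1 a procedure is not an AE in the first place, so on that reading the note exempts almost nothing. Its reference to hospitalization points straight at the criterion in 13.1.2, and a site could reasonably take it as cancelling that criterion. The trial plans 12–16 sites in eight countries; two workable readings are enough for inconsistent classification.

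The second reply is that many such events stay visible:
- Protocol Table 4 places an indicated hospitalization within Grade 3, so these events would ordinarily enter the Grade 3 and 4 tables.
- SAP 2.2.2 also gives the DSMB AEs by grade and an AE listing by participant.
- The ad hoc DSMB trigger in the protocol synopsis depends on grade and relatedness, not on seriousness.
- "All AESIs (related and not related) that occur after signing of the informed consent through 30 days after the last study visit, irrespective of grade" go to the sponsor within 24 hours.

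This largely stands up to the last visit, and it limits the harm. It does not restore the SAE label or 24-hour SAE handling for a non-AESI event, and it does not cover the 30 days after the last visit.

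**Conclusion.** The point holds as a conflict between two stated reporting rules, which must be reconciled. Sections 13.1.2 and 13.4 can give opposite answers for the same post-dose event. What is at risk is the SAE label and everything that follows from it and, for non-AESI events in the 30 days after the last visit, whether the event is recorded at all. The conclusion assumes that at least some sites read the note literally.

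The size of any under-reporting cannot be estimated from the documents. Two stronger inferences are tempting and unsupported:

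- *A quantified downward bias.* Assuming 1 to 4 affected infants would give 1/30 = 3.3 to 4/30 = 13.3 points, but that count has no source. The Phase 1 results in Protocol 5.4 do not supply one: 7 − 5 = 2 of 7 Cohort 2 infants not needing non-oral nutrition before dosing failed to maintain the ability to thrive, but this is a composite outcome, not a count of operations or admissions. The same section reports that 11 of 12 could still swallow well enough to feed orally.
- *Damage to the main safety result.* SAP 4.3 names unacceptable toxicity as the primary safety endpoint, defined by grade, relatedness, expectedness, symptoms and treatment. It does not depend on SAE status.

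**What to change.** Reconcile the two sections by replacing the note in 13.4 with:

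> A procedure is not itself an SAE. Hospitalization that the protocol requires, or for a procedure planned before informed consent for a pre-existing condition that has not worsened, is not by itself an SAE. An AE (a new or worsened condition) that requires or prolongs an in-patient stay, including for elective or minor surgery, is reported as an SAE under 13.1.2, with the condition as the event.

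Two features are deliberate. The last sentence requires an AE, so an admission without a new or worsened condition is not captured. The exclusion of protocol-required stays is needed because every infant is an in-patient from Day -1 to Day 3 (Protocol 7.1).

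Before database lock, check the procedures listed under SAP 7.4.2 against this wording and have sites reclassify where needed. The documents do not say whether that listing extends past the last visit, so sites should also be asked about the 30 days after it.

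The cost is a short amendment or clarification, a review of a listing for about 30 infants, and possibly a slightly higher reported SAE count. Assessments and patient care are unchanged.
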